9.6. Reporting of the related adverse events to the relevant authorities

Reporting of related AEs will be in accordance with applicable legal regulations.

If AE is deemed to be serious according to definition, the CRF are completed and Europharma (CRO) are notified immediately, not later than 24 hours after being informed of the SAE. Europharma will report these AEs to PLRP the next working day. PLRP send this data to the global PV Drug Safety, who will then submit it to the authorities.

Non serious AEs will be reported by Investigator in CRFs to Europharma. Europharma will report these AEs to PLRP once a month. PLRP send this data to the global PV Drug Safety, who will then submit it to the authorities.

10. STATISTICAL CONSIDERATIONS ON ADVERSE EVENTS

10.1. Patient classification and definition

The patient treated: Patient who received at least one dose of study drug.

10.2. Analysis, population, definition

Safety population: All patients who received at least one dose of study drug.

The safety data analysis will be conducted on the safety population.

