5. STUDY POPULATION

5.1 Records of participants in the study

Each Investigator will be required to keep list of patients included in the study. The list shall include the Patient name, initials and date of birth and must be kept confidentially at the study center.

The study is planned to include approximately 3,500 patients by Polish Oncologists and Urologists. Each physician participating in the study should make at least one follow-up.

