6. METHODOLOGY

6.1 Schedule of the study

Summary of observations and assessments in the implementation of this study are presented in the following table.

Table1. Schedule of the project

| Procedures for particular visits | Visit 1 | Visit 2* |
|--|---------|----------|
| Demographic data | Х | |
| Data on the primary disease | Х | |
| Qualification of patient to the non-interventional study (inclusion criteria) | Х | |
| History concerning the treatment of the primary disease before the administration of ZOLEDRONIC ACID ACTAVIS formulation | Х | |
| History concerning comorbidities and its treatment | Х | Х |
| History concerning course of treatment and the occurrence of possible adverse events of ZOLE- DRONIC ACID ACTAVIS formulation | Х | Х |
| History concerning tolerance of ZOLEDRONIC ACID ACTAVIS formulation in patient opinion | Х | Х |
| Recording of any changes in the drugs used in comorbidities therapy during treatment with ZOLE- DRONIC ACID ACTAVIS formulation | Х | Х |

* This visit will take place only if it is planned as a part of routine observation of the patient.

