7.2 Tolerance endpoints and methods of its evaluation

Data on adverse events and tolerability of treatment with **ZOLEDRONIC ACID ACTAVIS** in Patient opinion will be collected during the observation period as a response to the survey questions regarding these aspects during 1 single visit or 2 consecutive visits to specialist clinics.

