10.3. The method of determining the sample size

This is a non-interventional study in which the number of patients about 3,500 was determined taking into account the practical limitations, and not on the basis of statistical analysis. Therefore, this study does not make up the basis for the formulation of definitive conclusions about the safety of the study drug.

This is a descriptive study evaluating safety and tolerance of treatment with study drug, thus in this study basic statistical analysis will be performed.

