10.4. Statistical methods

On the basis of reported adverse events, the frequency of their occurrence in study population will be assessed. For the most common adverse events the characteristics of subpopulation in which it was reported will be analyzed.

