10.4.3. The safety assessment

All safety data will be included in the summaries of data on individual patients. Analysis and summary tables are based on data from the safety population

The related adverse events will be coded in accordance with Medical Dictionary for Regulatory Activities (Med-DRA).

The prevalence of all reported related adverse events and serious adverse events occurring during the study drug administration will be presented in the form of tables. In addition, summary tables will be presented, that will include data on the maximum severity, relationship to the study drug administration and related data on adverse events, and patients who discontinued treatment with study drug for any reason.

The related adverse events occurring during the study will be noted in the tables related to adverse events. Medication usage due to concomitant disease will be summarized with the number and percentage of patients receiving them divided into a group of pharmacological and generic name of the drug.

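### One-visit and two-visit patients share a single all-treated denominator, so related adverse events after Visit 1, mainly non-serious ones, are under-counted

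*Protocol*

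**What the plan says.** **Denominator.** Protocol Section 10.2 defines one analysis set: "Safety population: All patients who received at least one dose of study drug". Section 10.4.3 applies it throughout: "Analysis and summary tables are based on data from the safety population". Section 10.4 states the estimate: "On the basis of reported adverse events, the frequency of their occurrence in study population will be assessed". No other denominator and no person-time measure is given.

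**Follow-up.** Visit 2 is to fall at least two months after Visit 1 (Section 6.2.2). The footnote to Table 1 in Section 6.1 makes it conditional: "This visit will take place only if it is planned as a part of routine observation of the patient". Section 7.2 accepts data collected "during 1 single visit or 2 consecutive visits to specialist clinics". Section 5.1 adds "Each physician participating in the study should make at least one follow-up", which is worded per physician and does not make Visit 2 compulsory for each patient. Sections 3.3 and 3.3.1 nevertheless describe about four months of observation per patient.

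**Capture of events.** Related events are asked about at the visits, and the Visit 1 questions reach back before enrolment (Sections 6.2.1 and 7.1.2). Related serious events must be reported within 24 hours of the investigator learning of them (Sections 9.3.1, 9.4 and 9.6). Non-serious events reach the study organizer through the case report form (Section 9.6). Section 10.4.2 tabulates how many patients took part in later visits, but that count is not used as a denominator.

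**The concern.** Treatment must have started at least 30 days before enrolment (Section 5.2), so every enrolled patient has had a dose and the safety population is simply everyone enrolled. That set mixes patients observed at one visit with patients observed at two. For the one-visit patients there is no scheduled occasion after Visit 1 on which a non-serious event would be elicited and recorded. An event of that kind is lost from the numerator while the patient remains in the denominator.

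The frequency of related adverse events serves the main aim in Section 2.1. Missed events can only lower it, and a large sample does not reduce this kind of error. A reader of the tables would take the percentage to cover the roughly four months that the protocol says each patient is observed, which one-visit patients are not.

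**Working it through.** **Inputs from the protocol.** Planned size is about 3,500. There is no sample-size calculation to reproduce, because Section 10.3 says that "the number of patients about 3,500 was determined taking into account the practical limitations, and not on the basis of statistical analysis". The denominator is all treated patients, and Visit 2 is optional.

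**Inputs the protocol does not give (assumed).**
- P, the true proportion with a first related event from start of treatment to the end of observation: 10%, with 1.2% as a second case.
- f, the share of those first events that fall by Visit 1: 0, 0.5 or 0.8.
- m, the share of patients without Visit 2: 10% to 50%.

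**Formula.** Events up to Visit 1 are recorded for everyone. Later events are recorded only in the share 1 − m with Visit 2. If attendance is unrelated to risk and nothing after Visit 1 is captured without Visit 2,

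reported frequency = P × [f + (1 − f)(1 − m)].

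Example with f = 0.5 and m = 0.3: 10% × [0.5 + 0.5 × 0.7] = 8.5%.

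| True 10%, reported as | m = 10% | m = 20% | m = 30% | m = 50% |
|---|---|---|---|---|
| f = 0 | 9.0% | 8.0% | 7.0% | 5.0% |
| f = 0.5 | 9.5% | 9.0% | 8.5% | 7.5% |
| f = 0.8 | 9.8% | 9.6% | 9.4% | 9.0% |

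The f = 0 row is the extreme in which no first event precedes Visit 1. It also describes a table limited to events after Visit 1 but still divided by all treated patients.

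**Against sampling error.** At 10% and n = 3,500 the 95% half-width is 1.96 × √(0.10 × 0.90 / 3,500) = 1.0 percentage point. With f = 0.5 the shortfall equals this at m = 20% (1.0 point) and exceeds it at m = 30% (1.5 points). With f = 0.8 it reaches 1.0 point only at m = 50%.

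**Against the frequency classes in Section 1.2.** The common class starts at 1 in 100. With f = 0.5 a true 1.2% is reported as 1.2% × 0.85 = 1.02% at m = 30% and 1.2% × 0.75 = 0.90% at m = 50%, which is below the limit. With f = 0.8 it stays above the limit even at m = 50% (1.2% × 0.90 = 1.08%).

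**Effect of separate denominators.** Suppose 5% have an event by Visit 1, another 5% have a first event afterwards, and m = 30%. The pooled figure is (175 + 122.5) / 3,500 = 8.5%. Split by period, it is 175 / 3,500 = 5% and 122.5 / 2,450 = 5%, so both true values are recovered, provided that patients not seen have the same risk as those seen.

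**The case against.** The strongest reply is that one-visit patients are not treated as event-free, although a reader might infer this from Section 10.2 and the Visit 2 footnote. Visit 1 records their related events since the start of treatment, and Section 10.4.3 tabulates events during drug administration, so these patients contribute to numerator and denominator alike. Related serious events and related deaths do not depend on Visit 2, and Section 7.1.2 also obliges doctors to report related events they observe. This stands. It confines the problem to the time after Visit 1, and mainly to non-serious events. The fall from 10% to 5% therefore needs both f = 0 and half the patients without Visit 2. It would likewise be wrong to treat 1,750 as the effective sample for detecting serious events.

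A reader might also infer that the missed patients are those who deteriorate, which would make the shortfall larger. The documents do not settle this. Section 6.2.2 times visits by clinical need, so patients with problems could be more likely to be seen. Section 1.2 describes dosing every 3 to 4 weeks for prevention of skeletal events, so attendance could be high. The direction and strength of any selection are unknown.

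Finally, an all-treated safety set is standard, attendance is tabulated, finer tables could sit in an analysis plan that is not shown, and Section 10.3 disclaims definitive safety conclusions. These points lower the severity. They do not remove the issue, because the protocol itself fixes the set for the safety tables, and tabulating attendance shows the gap without correcting the frequencies.

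**Conclusion.** The point holds in limited form. Following the protocol as written under-counts related events after Visit 1, mainly non-serious ones, in patients without Visit 2. The fault is not the all-treated set in itself but its pairing with optional follow-up and no denominator for the patients actually followed.

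The size cannot be derived from the documents. Under the assumed ranges, the relative shortfall in the pooled frequency is (1 − f) × m: 5% to 25% of the true value when f = 0.5, and 2% to 10% when f = 0.8. These figures assume that attendance is unrelated to risk and that nothing is captured outside visits. For serious events the second assumption overstates the loss. The study is descriptive and no test or decision rule depends on the result, so this should be fixed, but it does not undermine the study as a whole.

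**What to change.** In Sections 10.2 and 10.4.3:

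- Tabulate related events up to Visit 1 over all enrolled patients.
- Tabulate events found at Visit 2 over patients who attended Visit 2. Attendance must define this denominator, not the presence of any later report. Otherwise a serious event reported without a visit would bring its own patient into the denominator, while event-free non-attenders stayed out, and the frequency would be pushed upwards.
- Add a rate per patient-month from start of treatment to the last study visit, with exact 95% intervals. The form must then hold treatment start, visit and event dates; the data list in Section 6.2.1 does not name them.
- Keep related serious events and the pooled percentage over all treated patients, and label the pooled figure as a lower bound for the period after Visit 1.
- Compare baseline characteristics and Visit 1 events between patients with and without Visit 2, because the split removes the bias only if the two groups have similar risk.

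The cost is some wording, possibly a few date fields and one more table set. Precision after Visit 1 falls: with 1,750 attenders, intervals are wider by a factor of √(3,500 / 1,750) = 1.41 than with 3,500. Reported frequencies will probably look slightly less favourable.

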10.3. The method of determining the sample size

This is a non-interventional study in which the number of patients about 3,500 was determined taking into account the practical limitations, and not on the basis of statistical analysis. Therefore, this study does not make up the basis for the formulation of definitive conclusions about the safety of the study drug.

This is a descriptive study evaluating safety and tolerance of treatment with study drug, thus in this study basic statistical analysis will be performed.

10.4. Statistical methods

On the basis of reported adverse events, the frequency of their occurrence in study population will be assessed. For the most common adverse events the characteristics of subpopulation in which it was reported will be analyzed.

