| DESIGN OF THE STUDY: | In the study will participated Oncologist and Urologist proving treatment of patients with advanced malignancies involving bone using ZOLEDRONIC ACID ACTAVIS formulation not less than 30 days prior to enrollment. Observing program will be implemented about 4 months. Data on the safety profile of ZOLEDRONIC ACID ACTAVIS formulation will be recorded in individual observation form (CRF) over two consecutive visits: the starting visit (first -1) and control visit (second -2) at least two months from the date of 1st visit. According to the date of the planned visit arising from clinical needs of the patient. |
| STUDY POPULATION: | Adults patients diagnosed with advanced malignancies involving bone (diagnosis according to ICD-10) in which by clinical indications at least 30 days prior to enrollment started therapy with ZOLEDRONIC ACID ACTAVIS formulation. |
| DRUG ASSESSED IN THE NON-INTERVEN- TIONAL STUDY: | ZOLEDRONIC ACID ACTAVIS 4 mg/5mL concentrate for solution for infusion contains in 1 mL concentrate 0.8 mg zoledronic acid (as monohydrate). It is sterile, clear and colorless concentration for solution for infusion. ZOLEDRONIC ACID ACTAVIS formulation indicated in prevention of skeletal related events (pathological fractures, spinal compression, radiation or surgery to bone, or tumor-induced hypercalcaemia) in adults patients with advanced malignancies involving bone as well as in treatment of adults patients with tumor-induced hypercalcaemia (TIH). |
| ENDPOINTS: | Safety endpoints and methods its evaluation: Collection of information on adverse events related to ZOLEDRONIC ACID ACTAVIS formulation treatment. Serious adverse events should be reported to EUROPHARMA immediately, not later than 24 hours after being informed of the SAE. This report does not relieve the doctor from the notification of adverse events in accordance with Art. 45a of the Act on the profession of doctor and dentist. |
| STATISTICAL METHODS: | A sample size of approximately 3,500 patients was based on the feasibility study. The data analysis obtained in the study will be descriptive: data sets will consist of summary statistics, such as numbers, mean values, standard deviation, median, minimum and maximum values observed frequency/ percentage. The safety analysis will be conducted on the safety population. |
| | |

| Procedures for particular visits | | Visit 2* |
|--|---|----------|
| Demographic data | х | |
| Data on the primary disease | х | |

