To prepare an infusion solution concerning 4 mg Zoledronic acid Actavis further dilute the Zoledronic acid Actavis concentrate (5,0 ml) with 100 ml calcium-free or other divalent cation-free infusion solution. If a lower dose of Zoledronic acid Actavis is required, first withdraw the appropriate volume as indicated below and then dilute it further with 100 ml of infusion solution. To avoid potential incompatibilities, the infusion solution used for dilution must be either 0.9% w/v sodium chloride or 5% w/v glucose solution.

Introduction for preparing reduced dose of Zoledronic acid Actavis:

Withdraw the appropriate volume of the liquid concentrate, as follows:

- » 4.4 ml for 3.5 mg dose
- » 4.1 ml for 3.3 mg dose
- » 3.8 ml for 3.0 mg dose

The solution containing zoledronic acid is given as a single 15-minute intravenous infusion in a separate infusion line. The hydration status of patients must be assessed prior to and following administration of Zoledronic acid Actavis to ensure that they are adequately hydrated.

Do not mix Zoledronic acid Actavis concentrate with calcium-containing or other divalent cation containing solution such as lactated Ringer's solution. Since no data are available on the compatibility of Zoledronic acid Actavis with other intravenously administered substances. Zoledronic acid Actavis must not be mixed with other medications/substances and should always be given through a separate infusion line.

For single use only. Any unused solution should be discarded. Only clear solution free from particles and discolouration should be used. Aseptic techniques must be followed during the preparation of the infusion.

Healthcare professionals are advised not to dispose of unused Zoledronic acid Actavis via the domestic sewage system. Any unused medicinal product or waste material should be disposed of in accordance with local requirements.

The recommended dose in the prevention of skeletal related events in patients with advanced malignancies involving bone is 4 mg zoledronic acid every 3 to 4 weeks. Patients should also be administered on oral calcium supplement of 500 mg and 400 IU vitamin D daily. The decision to treat patients with bone metastases for the prevention of skeletal related events should consider that the onset of treatment effect is 2-3 months.

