Standard hypercalcaemia-related metabolic parameters, such as serum levels of calcium, phosphate and magnesium, should be carefully monitored after initiating Zoledronic acid Actavis therapy. If hypocalcaemia, hypophosphataemia, or hypomagnesaemia occurs, short-term supplemental therapy may be necessary. Untreated hypercalcaemia patients generally have some degree of renal function impairment, therefore careful renal function monitoring should be considered. Case of severe hypocalcaemia requiring hospitalization have been reported. In some instances, life-threatening hypocalcaemia may be encountered.

Other products containing zoledronic acid as active substance are available for osteoporosis indications and treatment of Paget's disease of the bone. Patients being treated with Zoledronic acid Actavis should not be treated with such products or any other bisphosphonate concomitantly, since the combined effects of these agents are unknown.

The recommended dose in hypercalcaemia induced by malignance proces (albumin – corrected serum calcium ≥12.0 mh/dl or 3.0 mmol/l) is a single dose of 4 mg zoledronic acid.

Zoledronic acid Actavis treatment in TIH patients who also have severe renal impairment should be considered only after evaluating the risk and benefits of treatment. In the clinical studies, patients with serum creatinine >400 micromol/l or >4.5 mg/dl were excluded. No dose adjustment is necessary in TIH patients with serum creatinine < 400 micromol/l or <4.5 mg/dl.

Interaction of ZOLEDRONIC ACID ACTAVIS formulation with other medication products

In clinical studies, zoledronic acid has been administered concomitantly with commonly used anticancer agents, diuretics, antibiotics and analgesics without clinically apparent interactions occurring.

Zoledronic acid shows no appreciable binding to plasma proteins and does not inhibit human P450 enzymes in vitro, but no formal clinical interaction studies have been performed.

Caution is advised when bisphosphonates are administered with aminoglycosides, calcitonin or loop diuretics, since agents may have an additive effects, resulting in the lower serum calcium level longer periods than required.

Caution is indicated when Zoledronic acid Actavis is used with other potentially nephrotoxic medical products. Attention should also be paid to the possibility of hypomagnesaemia developing during treatment.

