1.3. The clinical reason for conducting this non-interventional study

ZOLEDRONIC ACID ACTAVIS is a generic formulation containing the active substance zoledronic acid monohydrate the first time used in the Polish population. This formulation obtained the registration in January 2013 and is available in commercially pharmacy, and its indications include the treatment of:

- prevention of skeletal related events (patholological fractures, spinal compression, radiation or surgery to bone, or tumor--induced hypercalcaemia) in adults patients with advanced malignancy involving bone,

- treatment of adult patients with tumor-induced hypercalcaemia (TIH).

It should be emphasized that the treatment with Zoledronic acid Actavis formulation in the prevention of skeletal complications in patients with advanced malignancies involving bone is a long process, therefore not only to minimize the symptoms of the disease, but also a good tolerance and acceptance of the therapy by the patient are important. Moreover, the use of zoledronic acid requires constant security monitoring.

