7.1 Safety endpoints and methods of its evaluation

7.1.2. Related adverse events

Data on adverse events related to treatment with **ZOLEDRONIC ACID ACTAVIS** will be collected during the observation period and will also include adverse events occurring before enrolment to the Study. Information on these events will be collected during visits to specialist clinics based on directly asked questions in the survey. Doctors are required to report observed related adverse events to [contact]. For further description on reporting of adverse events please see Section 9.

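### Crude adverse event percentages in one pooled population mix the drug's risk with uncapped prior exposure and unequal follow-up

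*Protocol*

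**What the plan says.** **Measure.** Section 10.4 states: "On the basis of reported adverse events, the frequency of their occurrence in study population will be assessed". The synopsis lists summary statistics ending in "median, minimum and maximum values observed frequency/ percentage". Section 10.4.3 will tabulate "The prevalence of all reported related adverse events and serious adverse events occurring during the study drug administration".

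**Denominator.** Section 10.2 defines one group: "Safety population: All patients who received at least one dose of study drug".

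**Exposure at entry.** Sections 5.2 and 5.3 set a floor of 30 days on treatment. Neither sets a ceiling.

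**Counting window.** Section 7.1.2 says that the related-event data "will also include adverse events occurring before enrolment to the Study". Section 9.1, by contrast, ties the on-treatment event to the active phase of the study, and one sentence of section 10.4.3 speaks of events arising during the study.

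**Follow-up.** The footnote to the schedule in section 6.1 makes Visit 2 conditional on routine care, and section 7.2 accepts data from one visit or two.

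**Regimens.** Section 1.2 says that the recommended dose for preventing skeletal events "is 4 mg zoledronic acid every 3 to 4 weeks", and that for tumour-induced hypercalcaemia it "is a single dose of 4 mg zoledronic acid".

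**Exposure data.** The schedule records the course of treatment at both visits, section 6.2.1 records data on treatment with the product, and section 12.1 requires use of the study drug to be recorded. None of these says whether first infusion date or infusion count is captured.

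**The concern.** The numerator can build up over a patient's whole time on the drug, while each patient counts once in the denominator. For an event that can occur at any infusion, a patient with many infusions has had more chances to contribute than one who has just passed 30 days. Two sets of sites using the same drug could then report different percentages only because one enrolled more long-term patients.

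The main aim in section 2.1 is the safety profile, and frequency is its stated summary. If the exposure behind that frequency is neither fixed nor shown, a reader cannot tell a high percentage from a long exposure, and a pattern by cumulative exposure would stay hidden.

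**Working it through.** **1. Figure to reproduce.** There is none. The only planned number is about 3,500 patients, which section 10.3 attributes to practical limits rather than a calculation. The check therefore asks how far the crude percentage can move when only the exposure mix changes.

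**2. Possible range of exposure.** Infusions = floor(days on drug / interval) + 1, with the 3- to 4-week interval of section 1.2.

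- At the 30-day minimum: floor(30/28) + 1 = 2 and floor(30/21) + 1 = 2. It is 1 under the single-dose regimen, if such a patient is enrolled.
- At the upper end: section 1.3 says "This formulation obtained the registration in January 2013". The protocol gives no study start date. The latest date it shows is that of the product summary cited in section 1.2, January 2015. Taking this as the start (an assumption) gives about 730 days: floor(730/28) + 1 = 27 and floor(730/21) + 1 = 35 infusions.

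The upper figures are a bound for uninterrupted treatment since registration, not a typical patient.

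**3. Crude percentage under two mixes.** Assume a constant, independent risk p per infusion. After k infusions, the share of patients with at least one event is 1 − (1 − p)^k. With a share w of patients at 2 infusions and the rest at K:

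crude = w[1 − (1 − p)^2] + (1 − w)[1 − (1 − p)^K]

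For p = 0.25%: 1 − 0.9975^2 = 0.50%, 1 − 0.9975^27 = 6.54% and 1 − 0.9975^13 = 3.20%.

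- K = 27, w = 0.8: 0.8 × 0.50 + 0.2 × 6.54 = 1.71%
- K = 27, w = 0.2: 0.2 × 0.50 + 0.8 × 6.54 = 5.33%

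The values of p and w are assumptions, so a range is shown:

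| p per infusion | K = 27, w = 0.8 → 0.2 | K = 13, w = 0.8 → 0.2 |
|---|---|---|
| 0.1% | 0.69% → 2.17% | 0.42% → 1.07% |
| 0.25% | 1.71% → 5.33% | 1.04% → 2.66% |
| 0.5% | 3.33% → 10.33% | 2.06% → 5.25% |
| 1% | 6.35% → 19.41% | 4.04% → 10.20% |

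The shift is about threefold with 27 infusions in the long group and about two and a half times with 13.

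**4. Compared with sampling error.** With n = 3,500, the 95% half-width 1.96 × √[c(1 − c)/3,500] is 0.43 points at c = 1.71% and 0.74 points at c = 5.33%. The shift of 3.62 points is several times larger.

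**5. An exposure-based rate.** For p = 0.25% and K = 27:

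- w = 0.8: 3,500 × (0.8 × 2 + 0.2 × 27) = 24,500 infusions and 61 expected events
- w = 0.2: 3,500 × (0.2 × 2 + 0.8 × 27) = 77,000 infusions and 193 expected events

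Both give 0.25 events per 100 infusions. Under this constant-risk assumption the rate does not depend on the mix.

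**6. Counter-check.** Hold the mix at 50/50 with K = 27 and double p from 0.25% to 0.5%. The crude figure rises from 3.52% to 6.83%, so it does respond to the drug's risk.

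**7. If only on-study events count.** On the narrower window of section 9.1, prior exposure matters less. But a patient seen only at Visit 1 has no planned data collection afterwards, while a patient with Visit 2 has at least two months of it, within an observation period of about four. A single percentage over both groups still pools unequal observation.

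**The case against.** Exposure-adjusted rates and tables by number of infusions are normal content for an analysis plan that is not shown here, and nothing in sections 10.2 or 10.4 forbids them. The point therefore cannot be that the protocol omits such tables. It rests on what the protocol fixes: no ceiling on prior treatment, a look-back before enrolment, an optional second visit, one pooled population and a percentage as the summary.

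Section 10.3 calls the study descriptive and disclaims definitive safety conclusions. That lessens the harm, but a descriptive percentage still needs a known exposure behind it.

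Treatment data are already collected. The Observation Form is not shown, so it cannot be said that infusion dates or counts are missing, only that the protocol does not name them.

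A reader might also infer more than the documents support:

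- **That the percentage reflects exposure rather than the drug.** It reflects both, as step 6 shows, and an event confined to the first infusion would not rise with infusion count at all.
- **That patients commonly have dozens of infusions, or that the estimate could run from 1.0% to 16.1%.** Those percentages compare 2 with 35 infusions at an assumed 0.5% risk. They describe two hypothetical patients, not a pooled estimate, and rest on an assumed start date and uninterrupted dosing.
- **That single-dose hypercalcaemia patients form a large share.** Hypercalcaemia is a labelled indication, but entry is by bone metastases, and sections 1.3 and 3.3 describe long-term therapy.
- **That results will be misplaced among the frequency classes of section 1.2.** No section plans that comparison.
- **That every pre-enrolment event certainly counts.** Section 7.1.2 says so, but sections 9.1 and 10.4.3 contain narrower wording.

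**Conclusion.** The point holds in this form: followed as written, the plan yields a percentage that combines the drug's risk with an uncapped distribution of prior exposure and with unequal follow-up. Which of these dominates depends on the counting window, which the protocol leaves in conflict.

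The illustrative size is 1.7% against 5.3% at an assumed 0.25% per infusion with a 27-infusion long group, or 1.0% against 2.7% with 13 infusions. These figures assume constant, independent risk per infusion and a swing from 80% to 20% short-exposed patients. The protocol gives neither the exposure distribution nor an expected risk, so they show what is possible, not what will occur. Since the study is descriptive and the remedy is small, this is a cheap improvement rather than a serious defect.

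**What to change.** 1. **Settle the counting window.** Reconcile sections 7.1.2, 9.1 and 10.4.3 on whether related events before enrolment enter the main tables. Either way, tabulate pre-enrolment and on-study related events separately, and show how many patients contribute one visit and how many two.
2. **Name the exposure fields.** State in sections 6.1 and 6.2 that the treatment data already recorded include date of first infusion and number of infusions up to each visit, with indication where available.
3. **Tie the tables to exposure.** In section 10.4.3 keep the percentage of patients, but show it by number of infusions (for example 1–2, 3–6, 7–12, more than 12) or by time on drug. Add related events per 100 infusions or per patient-year.

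The per-infusion rate averages early and late infusions and would dilute an event concentrated at the start, so it should be read beside the strata, not in place of them.

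The cost is slightly more chart abstraction, mainly at Visit 1, and a few more descriptive tables. No patient procedure is added. The form fields should be settled before data collection, because a later analysis plan can use only what was recorded.
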